#### 4.10.4. **Supportive Care Guidelines and Handling Immune Related AEs**

Subjects should receive appropriate supportive care measures as deemed necessary by the treating investigator. Suggested supportive care measures for the management of AEs with potential immunologic etiology are outlined below in section 6.2. Where appropriate, these guidelines include the use of oral or intravenous treatment with corticosteroids as well as additional anti-inflammatory agents if symptoms do not improve with administration of corticosteroids. Note that several courses of steroid tapering may be necessary as symptoms may worsen when the steroid dose is decreased. For each disorder, attempts should be made to rule out other causes such as metastatic disease or bacterial or viral infection, which might require additional supportive care. The treatment guidelines are intended to be applied when the investigator determines the events to be related to pembrolizumab and/or epacadostat. If after the evaluation the event is determined not to be related, the investigator does not need to follow the treatment guidance (as outlined below). It may be necessary to perform conditional procedures such as bronchoscopy, endoscopy, or skin photography as part of evaluation of the event.

Pembrolizumab may cause severe or life threatening infusion-reactions. Signs and symptoms usually develop during or shortly after drug infusion and generally resolve completely within 24 hours of completion of infusion. Dose modification and toxicity management guidelines on pembrolizumab associated infusion reaction are provided in Table 3.

**Table 3: Pembrolizumab Infusion Reaction Dose modification and Treatment Guidelines**

NCI CTCAE Grade	Treatment	Premedication at subsequent dosing
-----------------	-----------	------------------------------------

NCI CTCAE Grade	Treatment	Premedication at subsequent dosing

Grade 1 Mild reaction; infusion interruption not indicated; intervention not indicated
	
Increase monitoring of vital signs as medically indicated until the subject is deemed medically stable in the opinion of the investigator.
	
None

Grade 2 Requires infusion interruption but responds promptly to symptomatic treatment (e.g., antihistamines, NSAIDS, narcotics, IV fluids); prophylactic medications indicated for ≤ 24 hours
	
Stop Infusion and monitor symptoms. Additional appropriate medical therapy may include but is not limited to:
 
 
• IV fluids
 
• Antihistamines
 
• NSAIDS
 
• Acetaminophen
 
• Narcotics
 
 
Increase monitoring of vital signs as medically indicated until the subject is deemed medically stable in the opinion of the investigator. If symptoms resolve within one hour of stopping drug infusion, the infusion may be restarted at 50% of the original infusion rate (e.g., from 100 mL/hr to 50 mL/hr). Otherwise dosing will be held until symptoms resolve and the subject should be premedicated for the next scheduled dose. Subjects who develop Grade 2 toxicity despite adequate premedication should be permanently discontinued from further study treatment administration.
	
Subject may be premedicated 1.5h (± 30 minutes) prior to infusion of pembrolizumab (MK-3475) with:
 
Diphenhydramine 50 mg orally (or equivalent dose of antihistamine).
 
Acetaminophen 500-1000 mg orally (or equivalent dose of antipyretic).

Grades 3 or 4 Grade 3: Prolonged (i.e., not rapidly responsive to symptomatic medication and/or brief interruption of infusion); recurrence of symptoms
	
Stop Infusion. Additional appropriate medical therapy may include but is not limited to:
 
 
IV fluids
 
Antihistamines
 
NSAIDS
 
	
No subsequent dosing

NCI CTCAE Grade	Treatment	Premedication at subsequent dosing
following initial improvement; hospitalization indicated for other clinical sequelae (e.g., renal impairment, pulmonary infiltrates) Grade 4: Life-threatening; pressor or ventilatory support indicated	Acetaminophen Narcotics Oxygen Pressors Corticosteroids Epinephrine  Increase monitoring of vital signs as medically indicated until the subject is deemed medically stable in the opinion of the investigator. Hospitalization may be indicated. Subject is permanently discontinued from further study treatment administration.	
Appropriate resuscitation equipment should be available in the room and a physician readily available during the period of drug administration.		

Pembrolizumab may be interrupted for situations other than treatment-related AEs such as medical / surgical events or logistical reasons not related to study therapy. Subjects should be placed back on study therapy within 3 weeks of the scheduled interruption, unless otherwise discussed with the Sponsor. The reason for interruption should be documented in the patient's study record.

- Nausea/vomiting: Nausea and vomiting should be treated aggressively, and consideration should be given in subsequent cycles to the administration of prophylactic antiemetic therapy according to standard institutional practice. Subjects should be strongly encouraged to maintain liberal oral fluid intake.
- Anti-infectives: Subjects with a documented infectious complication should receive oral or IV antibiotics or other anti-infective agents as considered appropriate by the treating investigator for a given infectious condition, according to standard institutional practice.

#### 4.11. **Diet/Activity/Other Considerations**

##### 4.11.1. **Diet**

Subjects should maintain a normal diet unless modifications are required to manage an AE such as diarrhea, nausea or vomiting.

##### 4.11.2. **Contraception**

Pembrolizumab may have adverse effects on a fetus in utero. Furthermore, it is not known if pembrolizumab has transient adverse effects on the composition of sperm. For this study, male subjects will be considered to be of non-reproductive potential if they have azoospermia (whether due to having had a vasectomy or due to an underlying medical condition).

Female subjects will be considered of non-reproductive potential if they are either:

(1) postmenopausal (defined as at least 12 months with no menses without an alternative medical cause; in women < 45 years of age a high follicle stimulating hormone (FSH) level in the postmenopausal range may be used to confirm a post-menopausal state in women not using hormonal contraception or hormonal replacement therapy. In the absence of 12 months of amenorrhea, a single FSH measurement is insufficient);

OR

(2) had a hysterectomy and/or bilateral oophorectomy, bilateral salpingectomy or bilateral tubal ligation/occlusion, at least 6 weeks prior to screening;

OR

(3) has a congenital or acquired condition that prevents childbearing.

Female and male subjects of reproductive potential must agree to avoid becoming pregnant or impregnating a partner, respectively, while receiving study drug and for 120 days after the last dose of study drug by complying with one of the following:

(1) practice abstinence† from heterosexual activity;

OR

(2) use (or have their partner use) acceptable contraception during heterosexual activity.

Acceptable methods of contraception are‡:

Single method (one of the following is acceptable):

- intrauterine device (IUD)
- vasectomy of a female subject's male partner

- contraceptive rod implanted into the skin

Combination method (requires use of two of the following):

- diaphragm with spermicide (cannot be used in conjunction with cervical cap/spermicide)
- cervical cap with spermicide (nulliparous women only)
- contraceptive sponge (nulliparous women only)
- male condom or female condom (cannot be used together)
- hormonal contraceptive: oral contraceptive pill (estrogen/progestin pill or progestin-only pill), contraceptive skin patch, vaginal contraceptive ring, or subcutaneous contraceptive injection

†Abstinence (relative to heterosexual activity) can be used as the sole method of contraception if it is consistently employed as the subject's preferred and usual lifestyle and if considered acceptable by local regulatory agencies and ERCs/IRBs. Periodic abstinence (e.g., calendar, ovulation, sympto-thermal, post-ovulation methods, etc.) and withdrawal are not acceptable methods of contraception.

‡If a contraceptive method listed above is restricted by local regulations/guidelines, then it does not qualify as an acceptable method of contraception for subjects participating at sites in this country/region.

Subjects should be informed that taking the study medication may involve unknown risks to the fetus (unborn baby) if pregnancy were to occur during the study. In order to participate in the study subjects of childbearing potential must adhere to the contraception requirement (described above) from the day of study medication initiation (or 14 days prior to the initiation of study medication for oral contraception) throughout the study period up to 120 days after the last dose of study therapy. If there is any question that a subject of childbearing potential will not reliably comply with the requirements for contraception, that subject should not be entered into the study.

#### 4.11.3. Use in Pregnancy

If a subject inadvertently becomes pregnant while on treatment with pembrolizumab and/or Epcadostat, the subject will immediately be removed from the study. The site will contact the subject at least monthly and document the subject's status until the pregnancy has been completed or terminated. The outcome of the pregnancy will be reported to Merck and Incyte without delay if the outcome is a serious adverse experience (e.g., death, abortion, congenital

anomaly, or other disabling or life-threatening complication to the mother or newborn).

The study investigator will make every effort to obtain permission to follow the outcome of the pregnancy and report the condition of the fetus or newborn to Merck and Incyte. If a male subject impregnates his female partner, the study personnel at the site must be informed immediately and the pregnancy reported to Merck and Incyte and followed as described.

#### 4.11.4. Use in Nursing Women

It is unknown whether pembrolizumab nor Epcadostat is excreted in human milk. Since many drugs are excreted in human milk, and because of the potential for serious adverse reactions in the nursing infant, subjects who are breast-feeding are not eligible for enrollment.

#### 4.12. Subject Withdrawal/Discontinuation Criteria

Subjects may withdraw consent at any time for any reason or be dropped from the study at the discretion of the investigator should any untoward effect occur. In addition, a subject may be withdrawn by the investigator or the Sponsor if enrollment into the study is inappropriate, the study plan is violated, or for administrative and/or other safety reasons.

A subject must be discontinued from the study for any of the following reasons:

- The subject or legal representative (such as a parent or legal guardian) withdraws consent.
- Confirmed radiographic disease progression
  - Note:* For unconfirmed radiographic disease progression, please see Section 10.
  - Note:* A subject may be granted an exception to continue on treatment with confirmed radiographic progression if clinically stable or clinically improved
- Unacceptable adverse experiences
- Intercurrent illness that prevents further administration of treatment
- Investigator's decision to withdraw the subject
- The subject has a confirmed positive serum pregnancy test
- The subject is lost to follow-up
- Completed 24 months of uninterrupted treatment with pembrolizumab or 35 administrations of study medication, whichever is later.

*Note:* 24 months of study medication is calculated from the date of first dose. Subjects

who stop pembrolizumab after 24 months may be eligible for up to one year of additional study treatment if they progress after stopping study treatment provided they meet the requirements detailed in Section 4.8.

- Administrative reasons

The EOT and Follow-up visit procedures are listed in Section 9 (Study Calendar) and Section 4 (Visit Requirements). After the end of treatment, each subject will be followed up to 30 days or until new anti-cancer treatment is initiated, whichever occurs first for adverse event monitoring, including SAEs. Subjects who discontinue for reasons other than progressive disease will have post-treatment follow-up for disease status until disease progression, initiating a non-study cancer treatment, withdrawing consent or becoming lost to follow-up. After documented disease progression each subject will be followed by telephone for overall survival until death, withdrawal of consent, or the end of the study, whichever occurs first.

#### 4.12.1. **Discontinuation of Study Therapy after Complete Response**

Discontinuation of treatment may be considered for subjects who have attained a confirmed CR that have been treated for at least 24 weeks with pembrolizumab and epacadostat and had at least two treatments with pembrolizumab beyond the date when the initial CR was declared. Subjects who then experience radiographic disease progression may be eligible for up to one year of additional treatment with pembrolizumab and epacadostat via the Second Course Phase at the discretion of the investigator if no cancer treatment was administered since the last dose of pembrolizumab, the subject meets the safety parameters listed in the inclusion and exclusion criteria, and the study is open. Subjects will resume therapy at the same dose and schedule at the time of initial discontinuation.

#### 4.12.2. **Noncompliance with Oral Epacadostat Dosing**

Each patient will be given an oral medication diary to take home and record the dosing information including times of day and number of pills taken to ensure they are taking the medication as prescribed at home. Compliance of > 85% based on pill reconciliation and home diary entries at  $\geq 2$  consecutive visits will be strongly encouraged.

### **5. INVESTIGATIONAL AGENT/DEVICE/PROCEDURE INFORMATION**

#### **5.1. Investigational Products Description**

Detailed pharmaceutical and therapeutic background of pembrolizumab and epacadostat is provided in the respective IBs. The investigator shall take responsibility for and shall take all steps to maintain appropriate records and ensure appropriate supply, storage, handling, distribution and usage of investigational products in accordance with the protocol and any applicable laws and regulations.

##### **5.1.1. Epacadostat**

###### **5.1.1.1. Packaging, Labeling, and Preparation**

The study drug will be available as 100 mg tablets packaged in high-density polyethylene bottles. All tablet excipients comply with the requirements of the applicable compendial monographs (Ph. Eur., USP/NF). All Incyte investigational product labels will be in the local language and will comply with the legal requirements of each country.

###### **5.1.1.2. Storage and Stability**

Clinical supplies of epacadostat should be stored under ambient conditions, between 15°C to 30°C (59°F to 86°F). Study drug must be stored in a locked storage area with limited access. If epacadostat is exposed outside of the defined temperature ranges please quarantine the affected bottles and complete and submit the Temperature and Light Excursion Form (Appendix G) to Incyte according to the instructions on the form. Incyte will provide guidance as to whether the bottles will need to be destroyed based on the information that has been provided on the form.

If epacadostat is exposed outside of the defined temperature ranges please quarantine the affected bottles and complete and submit the Temperature and Light Excursion Form (Appendix G) to Incyte according to the instructions on the form. Incyte will provide guidance as to

whether the bottles will need to be destroyed based on the information that has been provided on the form.

### 5.1.2. **Pembrolizumab**

#### 5.1.2.1. **Packaging, Labeling, and Preparation**

Clinical supplies will be provided by Merck and will be affixed with a clinical label in accordance with regulatory requirements.

Details on preparation and administration of pembrolizumab (MK-3475) are provided in the Appendix F.

Product Name & Potency	Dosage Form
Pembrolizumab 100 mg/ 4mL	Solution for Injection

#### 5.1.2.2. **Storage and Stability**

Clinical supplies must be stored in a secure, limited-access location under the storage conditions specified on the label. Receipt and dispensing of study drug must be recorded by an authorized person at the study site. Clinical supplies may not be used for any purpose other than that stated in the Protocol.

Open-label vials of pembrolizumab should be stored between 2°C to 8°C (36°F to 46°F) in a locked storage area protected from light with limited access. Vials should be stored in the original box to ensure the drug product is protected from light. A maximum 12 hours of light exposure is permitted for the pembrolizumab vials.

Pembrolizumab solutions may be stored at room temperature for a cumulative time of up to 4 hours. This includes room temperature storage of drug product solution in vial, room temperature storage of admixture solution in the IV bags and the duration of infusion.

IV bags containing pembrolizumab may be stored under refrigeration at 2°C to 8°C (36°F to 46°F) for up to 20 hours. If refrigerated, allow the IV bags to come to room temperature prior to use.

## 5.2. Accountability, Handling, and Disposal of Epacadostat and Pembrolizumab

Responsibility for drug accountability at the study site rests with the investigator; however, the investigator may assign some of the drug accountability duties to an appropriate pharmacist or other designee. Inventory and accountability records must be maintained and readily available for inspection by any study monitor and are open to inspection at any time by any applicable regulatory authorities.

The investigator or designee will be expected to collect and retain all used, unused, and partially used containers of study drug according to their institution policies. The investigator or designee must maintain records that document:

- Delivery of study drug to the study site.
- Inventory of study drug at the site.
- Subject use of the study drug including pill or unit counts from each supply dispensed.
- Return of study drug to the investigator or designee by subjects.

These records should include dates, quantities, batch or serial numbers (if available), and the unique code numbers (if available) assigned to the investigational product and study subjects.

The investigational product must be used only in accordance with the protocol. The investigator will also maintain records adequately documenting that the subjects were provided the correct study drug specified.

Completed accountability records will be archived by the site. At the completion of the study, the investigator or designee will oversee destruction according to institutional standard operating procedures.

The investigator is responsible for keeping accurate records of the clinical supplies received from Merck or designee, the amount dispensed to and returned by the subjects and the amount remaining at the conclusion of the study.

Upon completion or termination of the study, all unused and/or partially used pembrolizumab will be destroyed at the site per institutional policy. It is the investigator's responsibility to

arrange for disposal of all empty containers, provided that procedures for proper disposal have been established according to applicable federal, state, local and institutional guidelines and procedures, and provided that appropriate records of disposal are kept.

## 6. DOSE MODIFICATIONS

### 6.1. Rationale for Dose Modification(s)

Subjects may require modification of epacadostat if necessitated by drug-related AEs, including irAEs; dose reductions of pembrolizumab are prohibited.

Epacadostat Dose Level Table	
Dose Level	Dose in mg
Starting Dose (0)	300mg BID
First Dose Reduction (-1)	200mg BID
Second Dose Reduction (-2)	100mg BID

Dosing interruptions are permitted in the case of medical / surgical events or logistical reasons not related to study therapy (e.g., elective surgery, unrelated medical events, patient vacation, and/or holidays). Subjects should be placed back on study therapy within 3 weeks (~ 21 days) of the scheduled interruption, unless otherwise discussed with Merck and Incyte. The reason for interruption should be documented in the patient's study record.

In some circumstances, it may be necessary to temporarily interrupt both study treatments as a result of AEs that may have an unclear relationship to study drug(s). Treatment with both study drugs should be withheld for drug-related Grade 4 hematologic toxicities, non-hematological toxicity  $\geq$  Grade 3 (including laboratory abnormalities), and severe or life-threatening AEs.

### 6.2. Dose Modifications of Pembrolizumab and Epacadostat

AEs (both non-serious and serious) associated with pembrolizumab and epacadostat exposure may represent an immunologic etiology. These adverse events may occur shortly after the first dose or several months after the last dose of treatment. Based on existing clinical trial data, most irAEs were reversible and could be managed with interruptions of pembrolizumab and

epacadostat, administration of corticosteroids and/or other supportive care. For suspected irAEs, ensure adequate evaluation to confirm etiology or exclude other causes. Based on the severity of irAEs, withhold or permanently discontinue pembrolizumab and epacadostat and administer corticosteroids. Dose modification and toxicity management guidelines for irAEs associated with pembrolizumab are provided in **Table 4**.

See Sections 4.10.4 for additional supportive care guidelines, including use of corticosteroids if necessary. Patients requiring treatment with corticosteroids for irAEs should be held through completion of taper, unless otherwise discussed and approved by Merck and Incyte.

In case toxicity does not resolve to Grade 1 within 12 weeks after last dose of study treatment should be discontinued only after consultation with Merck and Incyte. With investigator and Merck and Incyte agreement, subjects with a laboratory AE still at Grade 2 after 12 weeks may continue treatment in the study only if asymptomatic and controlled.

#### General Instructions for management of irAE

1. Corticosteroid taper should be initiated upon AE improving to Grade 1 or less and continue to taper over at least 4 weeks.
2. For situations where pembrolizumab has been withheld, pembrolizumab can be resumed after AE has been reduced to Grade 1 or 0 and corticosteroid has been tapered. For subjects with Grade 3 or 4 immune-related endocrinopathy, pembrolizumab may be resumed when AE improves to Grade 2 or lower and is controlled with hormonal replacement therapy.
3. For situation where pembrolizumab is withheld initially, pembrolizumab should be **permanently discontinued** if AE does not resolve within 12 weeks of last dose or corticosteroids cannot be reduced to  $\leq 10$  mg prednisone or equivalent per day within 12 weeks. However, subjects with asymptomatic
4. For severe and life-threatening irAEs, IV corticosteroid should be initiated first followed by oral steroid. Other immunosuppressive treatment should be initiated if irAEs cannot be controlled by corticosteroids

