**Table 4: Dose Modification Guidelines for Drug Immune-Related AEs associated with epacadostat and pembrolizumab**

**General instructions for AEs associated with Pembrolizumab:**

1. Corticosteroid taper should be initiated upon AE improving to Grade 1 or less and continue to taper over at least 4 weeks.
2. For situations where pembrolizumab has been withheld, pembrolizumab can be resumed after AE has been reduced to Grade 1 or 0 and corticosteroid has been tapered. Pembrolizumab should be permanently discontinued if AE does not resolve within 12 weeks of last dose or corticosteroids cannot be reduced to  $\leq 10$  mg prednisone or equivalent per day within 12 weeks.
3. For severe and life-threatening irAEs, IV corticosteroid should be initiated first followed by oral steroid. Other immunosuppressive treatment should be initiated if irAEs cannot be controlled by corticosteroids.

*The below table represents guidelines and are not required management for immune-related AEs and can be implemented at the discretion of the investigator. Specialist referral (Endocrinology, Pulmonary, GI, etc) is encouraged if questions arise about appropriate management.*

**Note:** Unless listed below, Grade 1 for all disease groups: continue therapy, treat symptoms, close monitoring for worsening symptoms, educate patient to report worsening immediately, if worsens: Treat as Grade (G) 2 or 3/4.

Toxicity	Hold Treatment For Grade	Management + Timing for Restarting Treatment	Follow-up	Treatment Discontinuation
Type 1 diabetes mellitus (if new onset) or Hyperglycemia	Type 1 diabetes mellitus (if new onset, including diabetic ketoacidosis [DKA]) or <math>\geq</math> Grade 3 Hyperglycemia, if associated with ketosis (ketonuria) or metabolic acidosis (DKA)	
 
- Delay therapy for new onset Type 1 diabetes mellitus or Grade 3-4 hyperglycemia associated with evidence of beta cell failure.
 
- Insulin replacement therapy is recommended for Type I diabetes mellitus and for Grade 3-4 hyperglycemia associated with metabolic acidosis or ketonuria.
 
- Evaluate patients with serum glucose and a metabolic panel, urine ketones, glycosylated hemoglobin, and C-peptide.
 
- Resume therapy when patients are clinically and metabolically stable
 
	
_____
	
Discontinue Pembrolizumab and Epacadostat if not clinically and metabolically stable

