Hyperthyroidism^1	Grade 2	
 
- Continue therapy.
 
- Non-selective beta blockers (e.g. propranolol) are suggested as initial therapy.
 
	
_____
	
_____

	Grade 3	
 
- Delay therapy
 
- Resume therapy with one dose reduction when toxicity resolves to Grade 0-1
 
-Treat with non-selective beta-blockers or thionamides as appropriate
 
- Treat with an initial dose of IV corticosteroid followed by oral corticosteroids. When symptoms improve to Grade 1 or less, steroid taper should be started and continued over no less than 4 weeks.
 
Replacement of appropriate hormones may be required as the steroid dose is tapered.
 
	
_____
	
Toxicity does not resolve within 12 weeks of last dose or inability to reduce corticosteroid to 10 mg or less of prednisone or equivalent per day within 12 weeks

		-Consider endocrine consult		
	Grade 4	
 
- Discontinue therapy permanently.
 
- Treat with an initial dose of IV corticosteroid followed by oral corticosteroids. When symptoms improve to Grade 1 or less, steroid taper should be started and continued over no less than 4 weeks.
 
- Consider endocrine consult
 
	_____	Permanently discontinue
Hypothyroidism^1	Grade 2-4	
 
- Continue therapy at same doses.
 
- Thyroid hormone replacement therapy, with levothyroxine or liothyronine, is indicated per standard of care.
 
-Consider endocrine consult for Grade 3-4
 
	_____	Discontinue Pembrolizumab and Epacadostat if not clinically and metabolically stable
Thyroid disorders can occur at any time during treatment. Monitor patients for changes in thyroid function (at the start of treatment, periodically during treatment, and as indicated based on clinical evaluation) and for clinical signs and symptoms of thyroid disorders				

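### Within Section 6.2, the general irAE instructions and Table 4 give conflicting stop and resume rules for severe hypophysitis and hyperthyroidism, with no stated precedence

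*Combined protocol and SAP*

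**What the plan says.** Section 6.2 deals with severe endocrine immune events in two places.

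**General Instructions for management of irAE, item 2.** The first sentence sets the ordinary threshold: "For situations where pembrolizumab has been withheld, pembrolizumab can be resumed after AE has been reduced to Grade 1 or 0", with the steroid tapered. The second sentence makes an exception: "For subjects with Grade 3 or 4 immune-related endocrinopathy, pembrolizumab may be resumed when AE improves to Grade 2 or lower". A further condition is that hormone replacement keeps the event under control. The sentence names both grades and excludes no type of endocrinopathy.

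**Table 4.** General instruction 2 at the head of the table repeats the ordinary threshold, "pembrolizumab can be resumed after AE has been reduced to Grade 1 or 0 and corticosteroid has been tapered", but not the exception. Among the endocrine rows:

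- Hypophysitis, Grades 3-4: "Discontinue therapy permanently".
- Hyperthyroidism, Grade 4: "Discontinue therapy permanently".
- Hyperthyroidism, Grade 3: delay, then "Resume therapy with one dose reduction when toxicity resolves to Grade 0-1".
- Hypothyroidism, Grades 2-4: "Continue therapy at same doses".
- New-onset type 1 diabetes or severe hyperglycemia: delay, then "Resume therapy when patients are clinically and metabolically stable".
- Suspected adrenal crisis: delay, with resumption possible once the patient is stable on low-dose steroid.

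A note closing Table 4 requires a permanent stop after any life-threatening event. The introduction to the table says that its content is guidance, to be applied at the investigator's discretion.

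**The concern.** The same section can send the same patient two ways. Under the general instructions, a severe endocrine event that has improved to Grade 2 on replacement may be followed by renewed pembrolizumab. Under Table 4, treatment may already have ended for good, or must wait for further improvement. At stake are the safety of a patient who is re-exposed, the benefit lost by a patient who is stopped, and whether treatment exposure in the trial reflects one rule or whichever text was consulted. Safety and tolerability is a secondary objective (Section 1.2), so consistent handling of severe immune events matters to the reading of the safety data.

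**Working it through.** There is no stated figure to reproduce and no arithmetic in the conflict itself. The check sets item 2 against each relevant part of Table 4.

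| Event | General instructions, item 2 | Table 4 | Result |
|---|---|---|---|
| Hypophysitis, Grade 3-4 | May resume at Grade 2 or lower on replacement | Permanent stop | Direct conflict |
| Hyperthyroidism, Grade 4 | Same | Permanent stop | Direct conflict |
| Hyperthyroidism, Grade 3 | Same | Resume at Grade 0-1 | Different threshold |
| Any Grade 3-4 endocrinopathy, under general instruction 2 of Table 4 | Same | Resume at Grade 0-1 after taper, no exception | Different threshold |
| Any Grade 4 endocrinopathy, under the closing note | Same | Permanent stop if life-threatening | Conflict |
| Hypothyroidism; type 1 diabetes or hyperglycemia; suspected adrenal crisis | Same | Continue, or delay and resume when stable | No automatic permanent stop in the row |

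Steps behind the table:

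1. *Same drug.* Item 2 concerns pembrolizumab. The title of Table 4 covers both study drugs, so its instructions on therapy include pembrolizumab.
2. *Grade 4 and the closing note.* Table 6 in Section 7.8 describes Grade 4 as life-threatening. Item 2 expressly lets Grade 4 endocrinopathy resume, while the closing note ends treatment.
3. *Test case.* A patient has Grade 3 hypophysitis and improves to Grade 2, controlled on replacement. Item 2 is met and pembrolizumab may resume. The hypophysitis row required a permanent stop at the outset. Both texts apply to this patient and give opposite answers.
4. *Precedence.* Section 6.2 says that the guidelines are provided in Table 4, and Section 6.3 refers to the table again. Neither says whether the row or the general instruction prevails.
5. *Reach into the analysis.* Sections 10.4 (Table 8) and 12.2.1 define PFS by progression or death, so stopping treatment is not an event. Section 4.6.2 continues imaging every 9 weeks after a stop for reasons other than progression. The design in Section 12.1 (30 patients, 20% against 39%, one-sided 10%) does not use these rules. Section 12.3 plans dose intensity, dose reductions and cycle delays, which depend on how such patients are handled.

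**The case against.** **Item 2 may apply only after a hold.** The text of Section 6.2 before the instructions distinguishes withholding from permanent discontinuation by severity, item 2 opens with cases where pembrolizumab was withheld, and its exception is permissive. On that reading a patient in a permanent-stop row never reaches item 2. This is the best harmonizing reading, but it does not clear the conflict. Section 6.1 withholds both drugs for drug-related non-hematologic toxicity of Grade 3 or above, so these patients have been withheld. Item 2 also names Grade 4 outright. And the Grade 3 hyperthyroidism row does provide for delay and resumption, yet at a different grade.

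**Hyperthyroidism may seldom satisfy item 2.** Item 2 requires control on hormone replacement, whereas the hyperthyroidism row relies on beta-blockers, thionamides and steroids and mentions replacement only as a possible need during the taper. This stands in part: the hyperthyroidism conflicts carry less practical weight. It does not touch hypophysitis, where Table 4 itself provides for replacement at Grade 2.

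**Table 4 is guidance, and the specific row overrides the general rule.** Discretion means that either course is open; it does not resolve the conflict. The documents state no rule of specificity, and the endocrinopathy sentence in item 2 is itself a specific exception.

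**There are controls.** Section 6.3 calls for immediate discussion with the sponsor of any irAE of Grade 2 or above. Table 6 requires both companies to approve in advance a rechallenge after a serious event possibly caused by drug. Table 4 asks for an endocrinology consultation for hypophysitis, and the study is at one institution. These limit the harm, but they do not tell those deciding which rule applies.

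**Such events may be few.** Section 2.2.4 lists the irAEs of Grade 3 or above among 56 patients on the combination as rash, raised AST and raised bilirubin, with no endocrinopathy. With 0 of 56, the one-sided 95% upper bound is 1 − 0.05^(1/56) = 5.2%, or 30 × 0.052 = 1.6 patients. Only 15 of the 56 were at 300 mg; 0 of 15 gives 1 − 0.05^(1/15) = 18.1%, or 30 × 0.181 = 5.4 patients. Those data are preliminary and unaudited, and the bound at the study dose is loose. Rarity lowers the priority but leaves the inconsistency.

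**Conclusion.** The inconsistency holds and should be corrected. It is a direct resume-or-stop conflict for hypophysitis of Grade 3-4 and hyperthyroidism of Grade 4, and through the closing note for other Grade 4 endocrinopathy if Grade 4 is taken as life-threatening, as Table 6 describes it. For Grade 3 hyperthyroidism, and between the two versions of general instruction 2, it is a conflict of threshold. Its weight lies in patient safety and consistent exposure.

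A reader might infer more than the documents support:

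- *That every severe endocrinopathy has contradictory stop rules.* The hypothyroidism, diabetes or hyperglycemia, and adrenal-crisis rows contain no automatic permanent stop.
- *That each affected patient shifts a planned discontinuation rate by 1/30 = 3.3 percentage points.* Section 12.3 plans no such rate. Its dose intensity is described by cycle and over cycles received, so a permanent stop may move it little.
- *That Table 4 governs.* Section 6.2 only refers to guidelines provided there.
- *That the primary endpoint is compromised.* The 6-month PFS definition and design figures do not depend on these rules.

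No view is taken on which rule is clinically right.

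**What to change.** Reconcile four texts into one rule per event and grade: item 2 of the general instructions in Section 6.2, general instruction 2 of Table 4, the hyperthyroidism and hypophysitis rows, and the closing note of Table 4. Alternatively, add a sentence stating which text prevails where they differ. The clinical content is for the sponsor to settle with the two drug suppliers.

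The cost is a wording amendment agreed with the suppliers and approved by the IRB, as Section 11.1 requires for any protocol change. Sample size, endpoints and planned analyses stay as they are.
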